## *2. Imputation step*

The imputation model implies a marginal multivariate normal distribution of the longitudinal outcome values across all visits based on a participant's assigned treatment arm and covariate values. This marginal imputation distribution will be used for all participants in the placebo arm and all participants in the active drug arm without an SDCR ICE. For participants in the active drug arm with an SDCR ICE, the mean of the marginal imputation distribution for outcomes after the SDCR ICE will be modified as per the CIR assumption ([Carpenter et al. 2013](#)).

For each participant, the conditional imputation distribution of their missing outcome values is defined as the marginal imputation distribution conditional on the participant's observed outcomes (including observed post-SDCR ICE outcome assessments). A single deterministic imputation using the conditional mean from the conditional imputation distribution for each participant with missing outcomes will be used.

## *3. Analysis step*

The completed data (using conditional mean imputation as described above) will be analyzed using an ANCOVA model with the change from baseline in CDR-SB at the Week 116 visit as the dependent variable. This analysis model includes treatment group as the primary covariate with adjustment for the same set of covariates as for the imputation model described above, namely baseline CDR-SB score, baseline ADAS-Cog 13 total score, baseline ADCS-ADL total score and the randomization stratification factors namely: disease stage (from eCRF), geographic region (from the IxRS), the use of AD medication at baseline (derived from eCRF based on a search of medications; see below for more details) and the APOE  $\epsilon$ 4 status (from the Vendor). For geographic region, IxRS is preferred over the eCRF source, to keep the "starting" region for analysis, in case a participant moved to a different region during the study (the eCRF would otherwise reflect the "final" region). AD medication at baseline will be defined as any use of donepezil, galantamine, memantine or rivastigmine prior to randomization and with an end date not before the randomization date. The primary treatment effect estimator is defined as the regression coefficient associated with the treatment group. The treatment effect will be reported as a difference in adjusted means. The treatment

effect at the other visits will be estimated in the same way and will be reported as supplementary analyses of the primary endpoint (see Section 5.3.5).

Percent relative difference, defined as 100 times the estimated treatment effect divided by *the absolute value of the* placebo arm estimate, will also be reported, for all visits, as a point estimate for descriptive purposes. Importantly, ANCOVA is applied to a complete dataset after appropriate missing data imputation. For complete data, ANCOVA applied to outcomes from a single visit is equivalent to a more complex MMRM model. It can be demonstrated that it leads to identical parameter estimates as a corresponding MMRM model with an arbitrary covariance structure if separate regression coefficients are estimated at different visits for all covariates (Amemiya 1985, p. 197).

#### 4. Inference step

Inference will be based on resampling techniques as recommended by von Hippel and Bartlett 2021. Specifically, the jackknife (Efron and Tibshirani, 1994) will be used to estimate the standard error of the primary treatment effect estimator and the test of the primary statistical hypothesis will be based on the corresponding Z-score. Compared to other resampling techniques, the jackknife has the advantage of providing a deterministic standard error estimate and, hence, removing any simulation randomness from the procedure.

##### 5.3.3.1 Software Implementation and Validation

The reference based imputation methodology will be implemented by an internally developed R package “rbmi” (“reference-based multiple imputation”). The package will comply with the ICH guidance document “ICH E 9: Statistical principles for clinical trials” which states that: “The computer software used for data management and statistical analysis should be reliable, and documentation of appropriate software testing procedures should be available.”

The testing strategy for the package consists of defining and documenting the expected input and output of each function and implementing unit tests to prove that the package performs as expected. All implemented methods will be recorded and referenced against the literature with unit tests and simulations put in place to show that known values can be recovered as well as showing consistency with similar software from other languages (most notably the “5-Macros” implemented by the Drug Information Association Scientific Working Group on Estimands and Missing Data in SAS).

The package, including all documentation and testing materials, is available on GitHub.com (<https://github.com/insightengineering/rbmi>) and on CRAN repository (<https://cran.r-project.org/package=rbmi>) to allow for unrestricted access and enable public scrutiny of the code and methods. Description of the rbmi package is also available on a published manuscript (Gower-Page et al. 2022).

The rbmi R package was validated by the in-house tool, Autovalidate R, which performs general R package quality checks and performs testing for expected behaviors.

### **5.3.4 Sensitivity Analyses for Primary Endpoint**

#### **Impact of COVID-19 pandemic**

The following sensitivity analyses will be performed to evaluate the impact of the COVID-19 pandemic:

- Vary threshold on number of missed dose-months due to the pandemic in the definition of “substantial reduction in drug exposure” ICE. The “substantial reduction in drug exposure” ICE is defined with a threshold  $\geq 4$  dose-months (not necessarily consecutive). A sensitivity analysis will be performed using different thresholds: 1, 2, 3, 5 and 6 dose-months. All other aspects of the primary estimator will remain the same.
- Exclude participants based on site closure information and apply a treatment policy strategy to all other COVID-19 related ICEs. In this analysis, all participants enrolled before a site closure due to the pandemic will be removed from the analysis set. In alignment with the primary estimand, only a site closure of 16 weeks or more during the double-blind treatment period and without any access to study drug (no home nursing) will be considered. In accordance with the FDA’s guidance for Industry “Statistical Consideration for Clinical Trial During the COVID-19 Public Health Emergency (June 2020)”, participants excluded from this analysis can be identified using baseline data only: randomization date and site number. The site closure information is an administrative site level information, independent of the conduct of the trial, collected using the eCRF for the purpose of this study and analysis. The substantial reduction in drug exposure due to the COVID-19 pandemic (defined as  $\geq 4$  missed dose-months) will not be considered as an ICE. All other aspects of the primary estimator will remain the same.
- Remote scale administration. Remote scale administration was authorized in exceptional cases at Weeks 104 and 116 visits due to COVID-19 related restrictions. In this analysis, all CDR-SB assessments performed remotely will be excluded from the analysis and treated as missing data. All other aspects of the primary estimator will remain the same.
- A subgroup analysis based on the date of randomization. This will allow estimating the treatment effect for subgroups of participants randomized at least 12 months before the onset of the global COVID pandemic (11 March 2020 according to the World Health Organization ([WHO](#)) opening remarks), in  $\geq 5$  to 12 months prior to the onset of the global COVID pandemic and within less than 5 months from the onset of the global COVID pandemic (see Section [5.3.5.1](#) for an exact definition of each subgroup).

## Impact of missing data handling methods

The following sensitivity analyses will be performed to evaluate the impact of missing data handling method:

- Tipping point analysis

This analysis stress tests the CIR assumption by imputing worse outcomes after SDCR ICEs in the active drug arm than predicted by the CIR assumption. This will be implemented via a marginal  $\delta$ -approach as described in the 'rbmi: advanced functionality' vignette of the rbmi's package and in Cro et al, 2020. Specifically, the imputation step will be performed as for the primary estimator and, after imputation is completed, a constant  $\delta$  will be added to the imputed week 116 outcomes occurring after SDCR ICEs in the active drug arm. The subsequent analysis step of these  $\delta$ -adjusted imputed datasets is as for the primary estimator.

To determine the tipping point, the constant  $\delta$  will be increased in small steps starting from a value of 0 (corresponding to the primary estimator). The tipping point will then be defined as the value of  $\delta$  at which the p-value for the treatment effect estimator first becomes greater than 5%.

## Impact of potential outliers or extreme observations

In order to assess the impact of a potentially small number of "extreme observations" or "outlier points" (e.g., rapid progressors) on the treatment effect, the ANCOVA analysis model will be replaced by a robust linear regression. Robust regression will produce treatment effect estimates less contaminated by highly influential observations. Specifically, robust regression using M estimation will be used. Standard errors and confidence intervals will be based on jackknife as described previously.

### 5.3.5 Supplementary Analyses for Primary Endpoint

#### 5.3.5.1 Subgroup Analyses for Primary Endpoint

The generalizability of the CDR-SB results when comparing the active drug arm to the placebo arm will be investigated by estimating the treatment effect in the following subgroups:

- Demographics:
  - Age, two age categories cut by the median
  - Sex
  - Geographic Region, as per IxRS
- Baseline disease severity:
  - CDR-GS = 0.5 vs CDR-GS > 0.5
  - Prodromal vs Mild (as per eCRF)

- APOE ε4 genotype
  - Carrier/Non Carrier
- Use of symptomatic AD medication at baseline Yes/No (derived from eCRF based on the search below)
  - Symptomatic AD medication is defined as any one of: donepezil, galantamine, memantine or rivastigmine
- Randomization date, three subgroups defined by the following dates:
  - *before* 11 March 2019
  - *in between* (and including) 11 March 2019 and 1 October 2019
  - *after* 1 October 2019

Summaries of the treatment effect for the change in CDR-SB from baseline to Week 116 by these subgroups will be provided in forest plots.

### **5.3.5.2 Other Supplementary Analyses for Primary Endpoint(s) Treatment effect estimates before Week 116**

In this supplementary analysis, the same analysis strategy as described for the primary estimator will be used to estimate the effect of the active drug on disease progression defined as a change in CDR-SB at other time points, other than Week 116.

The treatment effect on the adjusted mean change in CDR-SB from baseline to Week 24, 52, 76 and 104 will be provided.

#### ***Treatment effect in relationship to a post-baseline timepoint***

*In this supplementary analysis, the same analysis strategy as described for the primary estimator will be used to estimate the percent relative difference between Week 52 and Week 116 as well as between Week 24 and Week 116, and between Week 76 and Week 116.*

*The relative difference between e.g., Week 52 and Week 116 (and similarly for the other considered post-baseline timepoints) will be defined as:*

$$[(\text{Delta\_wk\_116} - \text{Delta\_wk\_52}) / (\text{Placebo\_wk\_116} - \text{Placebo\_wk\_52})] * 100$$

*where Delta\_wk\_x is the estimated treatment effect at Week x, and Placebo\_wk\_x is the estimated change from baseline for the placebo arm at Week x. All those quantities will be obtained from the same model used for the primary estimand.*

### **Treatment policy estimand**

All ICEs will be handled with a treatment policy strategy regardless of whether being SDCR or NSDCR. All observed data will be included regardless of occurrence of any ICE. Missing values following all ICEs will be imputed with the method used in the primary estimator for missing data following an SDCR ICE, see Section 5.3.3. Missing values, not following an ICE, will be imputed under MAR (similarly to the primary estimands analysis, see “Missing data assumptions for the primary estimator” in Section 5.3.3). Note that the attributes of population, variables, treatment, and population level summary will remain the same as for the primary estimand.

### **Concomitant AD treatment estimand**

In this supplementary analysis, the treatment effect will be evaluated in the hypothetical scenario that no post-baseline initiation or modification of the use of other approved AD medication has happened.

All attributes of this estimand except Treatment will be identical as for the primary estimator. The treatment attribute will be: “Prescribed study drug including uptitration to the target dose, irrespective of concomitant use of symptomatic treatment for AD at baseline, but assuming no initiation or change in symptomatic treatment after baseline”. In this supplementary analysis, all data following ICEs “Starting another treatment for AD” and “Changing the dose of a symptomatic treatment for AD” will be set to missing and imputed under a MAR assumption, in line with a hypothetical strategy. The analysis methods will be the same as described for the primary estimand.

### **MMRM**

This analysis aims to provide a reference point analysis method described in early versions of the protocol (up to version 4) and to other external analyses where MMRM was considered the default and primary analysis. All available data will be used in the analysis. There will be no missing data imputation or consideration for any intercurrent events. The model will include the following covariates: treatment group, visit, and treatment-by-visit interaction, baseline CDR-SB score and baseline CDR-SB score-by-visit interaction, baseline ADAS-Cog 13 total score, baseline ADCS-ADL total score and the randomization stratification factors, namely: disease stage (from eCRF), geographic region (from the IxRS), the use of AD medication at baseline (from eCRF) and the APOE ε4 status (from the Vendor). An unstructured variance-covariance structure will be applied to model the within-subject errors across visits. In the case of non-convergence, compound symmetry will be used, together with a robust estimator of standard error (“sandwich” estimator).

## **Clinically evident decline: a progressor analysis**

In this supplementary analysis, CDR-SB progression will be defined as a change from baseline in CDR-SB greater than or equal to a threshold  $x$ . The primary threshold of interest is  $x=2.5$ . The work justifying the threshold will be presented, as an oral presentation, at the Alzheimer's Association International Conference (AAIC), 31 July–4 Aug 2022; San Diego, CA and online (title of the oral presentation: *Selecting appropriate meaningful change thresholds for trials of early (prodromal-to-mild) AD: A caregiver-rated, anchor-based analysis based on the Tauriel Study*).

The CDR-SB progression endpoint will be analyzed using the same conditional mean imputed dataset as for the primary estimator of the primary estimand (Section 5.3.3).

The probability of CDR-SB progression by Week 116, in each treatment arm, will be estimated by the proportion of participants with a progression at any time during the double blinded period. The probability of progression by Week 116 will be obtained for different values of the progression threshold  $x$ . A plot of the probability of CDR-SB progression by Week 116 versus threshold values  $x$  will be generated.

In addition, a Cox proportional hazard model to estimate the treatment effect on time to first CDR-SB progression (based on the primary threshold of interest), may also be considered. In this case, the same baseline covariates as for the primary estimator of the primary estimand will be used (Section 5.3.3). An unadjusted model or a stratified analysis may be considered as well. Corresponding standard errors and confidence intervals will be calculated using the jackknife as previously described.

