#### *1. Imputation model*

The imputation model is a mixed effects model for repeated measures (MMRM) with the longitudinally assessed change from baseline in CDR-SB as the dependent variable. Its purpose is to estimate mean trajectories and covariance matrices of longitudinal outcomes in the placebo and active drug arms, respectively, while subjects remain on their randomized treatment. Therefore, all data after withdrawal from study treatment will be removed and considered as missing for the purpose of estimating the imputation model, and for this purpose only. If these data were not excluded, then the imputation model would estimate mean trajectories based on a mixture of observed pre- and post-discontinuation data. These would not be compatible with the CIR assumption employed in the subsequent imputation step, which requires combining mean trajectories while on active drug up to the ICE with increments while on placebo thereafter, respectively.

The imputation model includes the following covariates: treatment group, visit, and treatment-by-visit interaction, baseline CDR-SB score and baseline CDR-SB score-by-visit interaction, baseline ADAS-Cog 13 total score, baseline ADCS-ADL total score and the randomization stratification factors, namely: disease stage (from the eCRF), geographic region (from the IxRS), the use of AD medication at baseline (derived from the eCRF based on a search of medications; see below for more details) and the APOE  $\epsilon$ 4 status (from the Vendor). For geographic region, IxRS is preferred over the eCRF source, to keep the “starting” region for analysis, in case a participant moved to a different region during the study (the eCRF would otherwise reflect the “final” region). AD medication at baseline will be defined as any use of donepezil, galantamine, memantine or rivastigmine prior to randomization and with an

end date not before the randomization date. An unstructured variance-covariance structure will be applied to model the within-subject errors across visits. If the model fails to converge, then a heterogeneous Toeplitz covariance structure will be used instead and if this still fails, then a compound symmetry covariance structure will be used.

Imputations will be based on restricted maximum likelihood (REML) estimation of the regression and covariance parameters from the imputation model ([von Hippel and Bartlett 2021](#); [Wang and Robins 1998](#)).

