### **5.3.6 Convergence Considerations for RBMI-Based Analyses**

*In the rare situation that the imputation model (see step 1, imputation model, in Section 5.3.3) would fail to converge despite the attempt to simplify the variance-covariance*

matrix, it will be investigated whether removing some covariates and/or pooling factor levels of categorical covariates would solve the issue.

In case the root cause of the problem could not be attributed to the choice of covariates, the following approaches will be tried in sequence:

- *Replace jackknife with bootstrap, and accept up to a maximum of 5% failed runs (out of the total number of bootstrap runs). Runs that did fail would be discarded.*
- *Derive only a point estimate based on the conditional mean imputation, but no standard error (as jackknife and bootstrap did not work)*

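### The progressor analysis in SAP 5.3.5.2 applies a cutoff to single conditional-mean imputed CDR-SB values, which inflates the arm difference at the 2.5-point threshold by about 0.6 to 4.6 percentage points under Appendix 1 assumptions with 30% slowing

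*SAP*

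**What the plan says.** SAP 5.3.5.2 defines progression as a CDR-SB change from baseline of at least x, with x = 2.5 as the primary threshold. On the data to be used it says: "The CDR-SB progression endpoint will be analyzed using the same conditional mean imputed dataset as for the primary estimator of the primary estimand". Section 5.3.3 (Imputation step) describes that dataset: "A single deterministic imputation using the conditional mean from the conditional imputation distribution for each participant with missing outcomes will be used".

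The probability of progression in each arm is "estimated by the proportion of participants with a progression at any time during the double blinded period". It is also plotted against x, and a Cox model for time to first progression may be fitted. The paragraph on the Cox model ends: "Corresponding standard errors and confidence intervals will be calculated using the jackknife as previously described". Whether that sentence also covers the proportions is unclear.

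The dataset was built for a different target. In the Analysis step, "The primary treatment effect estimator is defined as the regression coefficient associated with the treatment group", taken from a linear ANCOVA. Appendix 1 supports the method with type I error simulations for that mean difference, all under the null. It simulates no threshold endpoint.

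**The concern.** A conditional mean is the centre of a participant's plausible outcomes. Averaging such values over participants gives the right mean. Asking whether each one exceeds a cutoff does not give the right proportion, since everyone predicted just above 2.5 counts as a certain progressor and everyone just below as a certain non-progressor. The jackknife estimates variance and cannot remove this bias.

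Clinically evident decline on the CDR is a declared exploratory endpoint (Protocol Table 2, SAP Table 1). It is absent from SAP Table 6, so 5.3.5.2 is where it is analysed. The threshold comes from meaningful-change work, so readers will use the result to judge clinical relevance.

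**Working it through.** The plan gives no numerical figure for this analysis, so I rebuilt the Appendix 1 design and checked it against the plan's own numbers.

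**1. Inputs**
- Design (SAP Section 3): placebo change 2.5, 30% slowing (difference 0.75), SD 2.97, two-sided 5%, 90% power. n per arm = 2 × (1.960 + 1.282)² × 2.97² / 0.75² = 330. Total 660, and 660 / (1 − 0.35) = 1015.4, i.e. the stated 1016, or 508 per arm.
- Placebo mean change at Week 116 (Appendix 1): 1 + 1.5 × 64/52 = 2.85. With 30% slowing: 0.7 × 2.85 = 1.99.
- SD of change at Week 116: √(1.53 + 4.26 − 2 × 0.52 × √(1.53 × 4.26)) = 1.77.
- Intercurrent event (ICE) models, 80% drop-out after study drug or condition related (SDCR) ICEs and 5% missed visits: Appendix 1.
- Appendix 1 places ICEs after each visit and lists baseline as a visit, so I ran two timings. ICEs after Weeks 24 to 116 reproduce Appendix 1 Table 3 within about 1.7 points. ICEs from baseline onward do so within about 2.5 points.

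**2. The mechanism by hand**

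Take a participant with average baseline and no later data, imputed under MAR.
- Residual SD at Week 116: √(4.26 × (1 − 0.52²)) = 1.76.
- Placebo: predicted 2.85, counted as a progressor with certainty. True probability at Week 116: Φ((2.85 − 2.5)/1.76) = 58%.
- Active: predicted 1.99, counted as a non-progressor with certainty. True probability: Φ((1.99 − 2.5)/1.76) = 39%.

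For such participants a true gap of 19 points becomes 100. The arm means lie on either side of 2.5, so the bias is upward. After an SDCR ICE, copy-increments imputation gives active participants the placebo slope, which narrows the gap between imputed means. This is consistent with the small shifts in Scenarios 3 and 4, which contain only SDCR ICEs.

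**3. Simulation**

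Placebo-minus-active difference in ever reaching 2.5, in percentage points (600,000 per arm, 30% slowing, continuous scores, imputation from CDR-SB only):

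| ICE timing | Scenario | Complete data | Conditional mean | Shift |
|---|---|---|---|---|
| After Weeks 24–116 | 1 | 16.66 | 19.24 | +2.6 |
| | 2 | 16.55 | 19.55 | +3.0 |
| | 3 | 16.41 | 17.38 | +1.0 |
| | 4 | 16.09 | 17.07 | +1.0 |
| From baseline | 1 | 16.35 | 20.83 | +4.5 |
| | 2 | 16.08 | 20.69 | +4.6 |
| | 3 | 15.67 | 16.64 | +1.0 |
| | 4 | 15.59 | 16.21 | +0.6 |

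Repeat runs of the last row gave +0.5 to +0.8. Most of the shift comes from undercounting active-arm progressors. In Scenario 2 from baseline, active falls from 52.3% to 48.2% while placebo moves from 68.4% to 68.9%.

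Standard error at 508 per arm: √((0.684 × 0.316 + 0.521 × 0.479)/508) = 3.0 points. The shift is therefore about 0.2 to 1.5 standard errors.

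Random draws from the same conditional distributions brought the difference to within about 0.15 point of complete data, which isolates the missing residual as the cause. Refitting the model in each of 300 trials at 508 per arm gave +2.4, +3.0, +0.9, +0.8 (later timing) and +4.2, +4.5, +0.9, +0.8 (from baseline).

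An unadjusted Cox hazard ratio shifts the same way. In Scenario 2 it goes from 0.641 to 0.590 (later timing) and from 0.645 to 0.571 (from baseline).

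**4. Sensitivity of the shift at 2.5**
- Extra covariates explaining 20% of residual variance (assumed): 0.7 to 2.8. Explaining 40%: 0.5 to 2.0.
- Drop-out of 40% after SDCR ICEs: 0.4 to 4.6.
- Scores on the 0.5-point grid: 0.7 to 5.0.
- 20% covariates, 40% drop-out and grid together: 0.3 to 2.7.
- SD of change rescaled to 2.97: 0.5 to 4.2.
- 10% slowing: about 0 to 1.6. 40% slowing: 0.8 to 4.9.
- No drug effect: at most 0.8 in size.

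At x = 4 (my choice, since the plan plots a range but names only 2.5), progression is understated by about 3 to 6 points in each arm. With no effect and unequal ICE rates (Scenarios 2 and 4), a spurious 0.9 to 2.0 points favours active.

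**The case against.** The mechanism is hard to dispute; the size is not.
- **Timing.** The figures above 3 points need ICEs starting at baseline. That timing overstates the ICEs not related to study drug or condition, which drive the large shifts: in Scenario 2, 10.4% and 14.5% against 9% and 12% in Table 3. The later timing gives 8.8% and 12.1%, although the baseline timing fits some SDCR rates slightly better.
- **Covariates.** The plan's model also uses "baseline ADAS-Cog 13 total score, baseline ADCS-ADL total score and the randomization stratification factors", which my main runs omit. With 20% of residual variance explained and the later timing, the shift is about 0.7 to 2.2 points, below one standard error.
- **Inputs.** The 80% drop-out is a type I error setting, not a forecast, and participants who stop treatment are asked to keep attending.
- **Consequence.** The analysis is supplementary, no test of the proportions is specified, and the Cox model is optional.
- **Remedy.** Section 5.3.6 ("Replace jackknife with bootstrap, and accept up to a maximum of 5% failed runs") offers the bootstrap only when the imputation model fails to converge, so it is no precedent here.

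These points stand as limits on size and priority, and they favour the lower part of the range. They do not rescue the method: the shift was upward at 30% slowing in every setting, and no provision in the SAP corrects it.

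**Conclusion.** The concern holds. Section 5.3.5.2 prescribes a biased estimator for the progression proportions, the threshold plot and any Cox model. With a true 30% slowing and Appendix 1 ICE rates, the difference at 2.5 is overstated by about 1 to 3 points with ICEs after Weeks 24 to 116, and by 0.6 to 4.6 points with ICEs from baseline. The plan's covariates would probably reduce this, by an amount the documents do not let me fix. The size grows with the true effect and with the share of values imputed under MAR. At 2.5 the bias exaggerates a real effect but does not create one. The primary result is unaffected. It should be fixed, because the endpoint bears on clinical relevance and the bias is avoidable.

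**What to change.** In SAP 5.3.5.2, keep the imputation model and the CIR and MAR rules, but impute by random draws that include residual variation (for example at least 100 datasets with a fixed seed). Apply the threshold within each dataset and average the estimates. Use this for the proportions, the threshold plot and any Cox model. State whether draws are rounded to 0.5-point CDR-SB steps before thresholding, and which analyses the standard-error sentence covers.

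For these analyses, replace the jackknife with a bootstrap that refits the imputation model and re-imputes in each resample. In a check of 60 trials per setting with 60 resamples each, this gave mean standard errors of 2.9 to 3.0 against an empirical SD of 2.8 to 3.0, with 93% to 97% coverage. The primary ANCOVA keeps its conditional-mean dataset and jackknife.

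The cost is a short paragraph and more computing. The property the plan values ("Compared to other resampling techniques, the jackknife has the advantage of providing a deterministic standard error estimate") is given up for this one supplementary analysis, and the reported difference at 2.5 will probably be smaller.
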